7.5 RETENTION OF RECORDS

Records and documents pertaining to the conduct of this study and the distribution of IMP, including eCRFs, electronic or paper PRO data (if applicable), Informed Consent Forms, laboratory test results, and medication inventory records, must be retained by the Principal Investigator for at least 15 years after completion or discontinuation of the study or for the length of time required by relevant national or local health authorities, whichever is longer. After that period of time, the documents may be destroyed, subject to local regulations.

No records may be disposed of without the written approval of the Sponsor. Written notification should be provided to the Sponsor prior to transferring any records to another party or moving them to another location.

8. ETHICAL CONSIDERATIONS

8.1 COMPLIANCE WITH LAWS AND REGULATIONS

This study will be conducted in full conformance with the ICH E6 guideline for Good Clinical Practice and the principles of the Declaration of Helsinki, or the laws and regulations of the country in which the research is conducted, whichever affords the greater protection to the individual. The study will comply with the requirements of the ICH E2A guideline (Clinical Safety Data Management: Definitions and Standards for Expedited Reporting). Studies conducted in the United States or under a U.S. Investigational New Drug (IND) application will comply with U.S. Food and Drug Administration regulations and applicable local, state, and federal laws. Studies conducted in the European Union or European Economic Area will comply with the E.U. Clinical Trial Directive (2001/20/EC).

8.2 INFORMED CONSENT

The Sponsor's sample Informed Consent Form (and ancillary sample Informed Consent Forms such as a Child's Informed Assent Form or Mobile Nursing Informed Consent Form, if applicable) will be provided to each site. If applicable, it will be provided in a certified translation of the local language. The Sponsor or its designee must review and approve any proposed deviations from the Sponsor's sample Informed Consent Forms or any alternate consent forms proposed by the site (collectively, the "Consent Forms") before IRB/EC submission. The final IRB/EC-approved Consent Forms must be provided to the Sponsor for health authority submission purposes according to local requirements.

If applicable, the Informed Consent Form will contain separate sections for any optional procedures. The investigator or authorized designee will explain to each patient the objectives, methods, and potential risks associated with each optional procedure. Patients will be told that they are free to refuse to participate and may withdraw their consent at any time for any reason. A separate, specific signature will be required to document a patient's agreement to participate in optional procedures. Patients who decline to participate will not provide a separate signature.

The Consent Forms must be signed and dated by the patient or the patient's legally authorized representative before his or her participation in the study. The case history or clinical records for each patient shall document the informed consent process and that written informed consent was obtained prior to participation in the study.

The Consent Forms should be revised whenever there are changes to study procedures or when new information becomes available that may affect the willingness of the patient to participate. The final revised IRB/EC-approved Consent Forms must be provided to the Sponsor for health authority submission purposes.

Patients must be re-consented to the most current version of the Consent Forms (or to a significant new information/findings addendum in accordance with applicable laws and IRB/EC policy) during their participation in the study. For any updated or revised Consent Forms, the case history or clinical records for each patient shall document the informed consent process and that written informed consent was obtained using the updated/revised Consent Forms for continued participation in the study.

A copy of each signed Consent Form must be provided to the patient or the patient's legally authorized representative. All signed and dated Consent Forms must remain in each patient's study file or in the site file and must be available for verification by study monitors at any time.

For sites in the United States, each Consent Form may also include patient authorization to allow use and disclosure of personal health information in compliance with the U.S. Health Insurance Portability and Accountability Act (HIPAA) of 1996. If the site utilizes a separate Authorization Form for patient authorization for use and disclosure of personal health information under the HIPAA regulations, the review, approval, and other processes outlined above apply except that IRB review and approval may not be required per study site policies.

8.3 INSTITUTIONAL REVIEW BOARD OR ETHICS COMMITTEE

This protocol, the Informed Consent Forms, any information to be given to the patient, and relevant supporting information must be submitted to the IRB/EC by the Principal Investigator and reviewed and approved by the IRB/EC before the study is initiated. In addition, any patient recruitment materials must be approved by the IRB/EC.

The Principal Investigator is responsible for providing written summaries of the status of the study to the IRB/EC annually or more frequently in accordance with the requirements, policies, and procedures established by the IRB/EC. Investigators are also responsible for promptly informing the IRB/EC of any protocol amendments (see Section 9.6).

In addition to the requirements for reporting all adverse events to the Sponsor, investigators must comply with requirements for reporting serious adverse events to the local health authority and IRB/EC. Investigators may receive written IND safety reports or other safety-related communications from the Sponsor. Investigators are responsible for ensuring that such reports are reviewed and processed in accordance with health authority requirements and the policies and procedures established by their IRB/EC, and archived in the site's study file.

8.4 CONFIDENTIALITY

The Sponsor maintains confidentiality standards by coding each patient enrolled in the study through assignment of a unique patient identification number. This means that patient names are not included in data sets that are transmitted to any Sponsor location.

Patient medical information obtained by this study is confidential and may be disclosed to third parties only as permitted by the Informed Consent Form (or separate authorization for use and disclosure of personal health information) signed by the patient, unless permitted or required by law.

Medical information may be given to a patient's personal physician or other appropriate medical personnel responsible for the patient's welfare, for treatment purposes.

Given the complexity and exploratory nature of the analyses, data derived from exploratory biomarker specimens will generally not be provided to study investigators or patients unless required by law. The aggregate results of any conducted research will be available in accordance with the effective Sponsor policy on study data publication (see Section 9.5).

Data generated by this study must be available for inspection upon request by representatives of national and local health authorities, Sponsor monitors, representatives, and collaborators, and the IRB/EC for each study site, as appropriate.

8.5 FINANCIAL DISCLOSURE

Investigators will provide the Sponsor with sufficient, accurate financial information in accordance with local regulations to allow the Sponsor to submit complete and accurate financial certification or disclosure statements to the appropriate health authorities. Investigators are responsible for providing information on financial interests during the course of the study and for 1 year after completion of the study (see definition of end of study in Section 3.2).

9. STUDY DOCUMENTATION, MONITORING, AND ADMINISTRATION

9.1 STUDY DOCUMENTATION

The investigator must maintain adequate and accurate records to enable the conduct of the study to be fully documented, including, but not limited to, the protocol, protocol amendments, Informed Consent Forms, and documentation of IRB/EC and governmental approval. In addition, at the end of the study, the investigator will receive the patient data, including an audit trail containing a complete record of all changes to data.

9.2 PROTOCOL DEVIATIONS

The investigator should document and explain any protocol deviations. The investigator should promptly report any deviations that might have an impact on patient safety and data integrity to the Sponsor and to the IRB/EC in accordance with established IRB/EC policies and procedures. The Sponsor will review all protocol deviations and assess whether any represent a serious breach of Good Clinical Practice guidelines and require reporting to health authorities. As per the Sponsor's standard operating procedures, prospective requests to deviate from the protocol, including requests to waive protocol eligibility criteria, are not allowed.

9.3 SITE INSPECTIONS

Site visits will be conducted by the Sponsor or an authorized representative for inspection of study data, subjects' medical records, and eCRFs. The investigator will permit national and local health authorities; Sponsor monitors, representatives, and collaborators; and the IRBs/ECs to inspect facilities and records relevant to this study.

9.4 ADMINISTRATIVE STRUCTURE

The study will be conducted globally and include approximately 240 patients. The contract research organization [REDACTED] will be responsible for submission to IRB/ECs for approval of the study protocol, patient recruitment, study conduct, data collection, and reporting.

9.5 PUBLICATION OF DATA AND PROTECTION OF TRADE SECRETS

Regardless of the outcome of a trial, the Sponsor is dedicated to openly providing information on the trial to healthcare professionals and to the public, both at scientific congresses and in peer-reviewed journals. The Sponsor will comply with all requirements for publication of study results. For more information, refer to the Roche Global Policy on Sharing of Clinical Trials Data at the following Web site:

www.roche.com/roche_global_policy_on_sharing_of_clinical_study_information.pdf

The results of this study may be published or presented at scientific congresses. For all clinical trials in patients involving an IMP for which a marketing authorization application has been filed or approved in any country, the Sponsor aims to submit a journal manuscript reporting primary clinical trial results within 6 months after the availability of the respective Clinical Study Report. In addition, for all clinical trials in patients involving an IMP for which a marketing authorization application has been filed or approved in any country, the Sponsor aims to publish results from analyses of additional endpoints and exploratory data that are clinically meaningful and statistically sound.

The investigator must agree to submit all manuscripts or abstracts to the Sponsor prior to submission for publication or presentation. This allows the Sponsor to protect proprietary information and to provide comments based on information from other studies that may not yet be available to the investigator.

In accordance with standard editorial and ethical practice, the Sponsor will generally support publication of multicenter trials only in their entirety and not as individual center data. In this case, a coordinating investigator will be designated by mutual agreement.

Authorship will be determined by mutual agreement and in line with International Committee of Medical Journal Editors authorship requirements. Any formal publication of the study in which contribution of Sponsor personnel exceeded that of conventional monitoring will be considered as a joint publication by the investigator and the appropriate Sponsor personnel.

Any inventions and resulting patents, improvements, and/or know-how originating from the use of data from this study will become and remain the exclusive and unburdened property of the Sponsor, except where agreed otherwise.

9.6 PROTOCOL AMENDMENTS

Any protocol amendments will be prepared by the Sponsor. Protocol amendments will be submitted to the IRB/EC and to regulatory authorities in accordance with local regulatory requirements.

Approval must be obtained from the IRB/EC and regulatory authorities (as locally required) before implementation of any changes, except for changes necessary to eliminate an immediate hazard to patients or changes that involve logistical or administrative aspects only (e.g., change in Medical Monitor or contact information).

Appendix 1 Schedule of Activities

Study Week	Treatment															SFU	UV ^d	FV ^e	ET
	0 ^{a, b}	1 ^c	4	8	12 ^a	16	20	24 ^a	28	32	36 ^a	40	44	48 ^a	56				
Day (Visit Window)	1	8 (±1)	29 (±4)	57 (±4)	85 (±4)	113 (±4)	141 (±4)	169 (±4)	197 (±7)	225 (±7)	253 (±7)	281 (±7)	309 (±7)	337 (±7)	393 (±7)				
Informed consent ^f	x																		
Eligibility criteria	x																		
Concomitant medications ^g	x	x	x	x	x	x	x	x	x	x	x	x	x	x	x	x	x	x	
Adverse events	x	x	x	x	x	x	x	x	x	x	x	x	x	x	x	x	x	x	
Vital signs ^h	x		x	x	x			x			x			x	x	x	x	x	
Weight	x		x		x			x			x			x	x	x	x	x	
Height	x																		
Complete PE ⁱ	x																		
Limited PE ^j			x	x	x			x			x			x	x	x	x	x	
MTB screening ^k	x																		
Viral Serology ^l	x																		
12-Lead ECG ^m	x		x					x						x	x	x		x	
CK, aldolase, and LDH ⁿ	x															x	x		
Direct Coombs test ^o	x		x	x	x			x			x			x	x	x	x	x	
Hematology ^p	x		x	x	x	x	x	x	x	x	x	x	x	x	x	x	x	x	
Chemistry panel ^q	x		x	x	x	x	x	x	x	x	x	x	x	x	x	x	x	x	
Coagulation panel ^r	x							x						x		x		x	

Appendix 1 Schedule of Activities (cont.)

Study Week	Treatment															SFU	UV ^d	FV ^e	ET
	0 ^{a, b}	1 ^c	4	8	12 ^a	16	20	24 ^a	28	32	36 ^a	40	44	48 ^a	56				
Day (Visit Window)	1	8 (±1)	29 (±4)	57 (±4)	85 (±4)	113 (±4)	141 (±4)	169 (±4)	197 (±7)	225 (±7)	253 (±7)	281 (±7)	309 (±7)	337 (±7)	393 (±7)				
Total Ig, IgG, IgM, IgE, IgA ^s	x				x			x			x			x	x	x	x	x	
CRP	x		x		x			x			x			x	x	x	x	x	
Pregnancy test ^t	x		x	x	x	x	x	x	x	x	x	x	x	x	x	x	x	x	
TBNK	x		x		x			x			x			x	x	x	x	x	
ESR (on site or at local laboratory)	x		x					x			x			x		x	x	x	
Urinalysis ^u	x		x	x	x			x			x			x	x	x	x	x	
C3, C4, CH50 ^v	x		x	x	x			x			x			x	x	x	x	x	
Autoantibody panel ^w	x							x						x					
Anti-dsDNA	x		x	x	x			x			x			x	x	x	x	x	
Protein creatinine ratio ^x	x		x	x	x			x			x			x	x		x	x	
Plasma PK sample ^y	x							x						x		x	x	x	
BILAG-2004	x		x	x	x			x			x			x	x	x	x	x	
SLEDAI-2K and SFI	x		x	x	x			x			x			x	x	x	x	x	
GTCl and fasting lipids ^z	x				x			x			x			x					
SLICC damage index	x							x						x					
CLASI	x		x		x			x			x			x	x	x	x	x	
Optional photographic documentation ^{aa}	x		x		x			x			x			x	x	x	x	x	

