2. OBJECTIVES AND ENDPOINTS

This OLE study will evaluate the long-term safety and efficacy of GDC-0853 in patients with moderate to severe active SLE. Specific objectives and corresponding endpoints for the study are outlined below.

Table 1 Objectives and Corresponding Endpoints

Objectives	Corresponding Endpoints
Primary Objective (Safety)	

To evaluate the long-term safety of GDC-0853 over an extended treatment period of up to 48 weeks	
The nature, frequency, severity, and timing of adverse eventsChanges in vital signs, physical findings, ECGs, and clinical laboratory results during and following GDC-0853 administration
Secondary Objective (Efficacy)	

To evaluate the clinical efficacy of GDC-0853 in combination with SOC over time	
SRI-4 response up to Week 48
Exploratory Efficacy Objectives	

To evaluate if GDC-0853 leads to decreased steroid usage and is steroid sparing	
Change in cumulative steroid dose use up to Week 48To assess glucocorticoid toxicity at Weeks 12, 24, 36, and 48 using the GTCI

To evaluate the ability of GDC-0853 to prolong the time to first SLE flare and reduce the number of total SLE flares	
Flares as defined by the SFI and BILAG during the OLE study

Table 1 Objectives and Corresponding Endpoints (cont.)

Objectives	Corresponding Endpoints
Exploratory Efficacy Objectives (cont.)	

 To evaluate the ability of GDC-0853 to prevent systemic damage 	
 Change in SLICC/ACR Damage Index up to Week 48

 To evaluate the ability of GDC-0853 to improve cutaneous manifestations of SLE 	
 Change in CLASI Total Activity Score up to Week 48

 To evaluate the ability of GDC-0853 to improve Patient's Global Assessment 	
 Change in Patient's Global Assessment of disease activity up to Week 48
Pharmacokinetic Objective	

 To characterize the pharmacokinetics of GDC-0853 in patients using a population PK approach 	
 Steady-state PK parameters: AUC_{0-t}, C_{trough}, $t_{1/2}$, and apparent CL/F

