4.4.5.4 SLICC/ACR Damage Index for Systemic Lupus Erythematosus

The SLICC/American College of Rheumatology (ACR) Damage Index for SLE will be utilized to assess organ damage as opposed to the collection of disease activity (see [Appendix 8](#)). Damage is defined as non-reversible change not related to active inflammation.

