4.5 TREATMENT, PATIENT, STUDY, AND SITE DISCONTINUATION

4.5.1 Study Treatment Discontinuation

Patients must discontinue study treatment and return for a safety follow-up visit if they experience any of the following (see [Table 3](#)):

- Requirement of any prohibited medication as defined in [Section 4.3.2](#)
- Treated with accepted immunosuppressant that exceeds the maximum dose as defined by the protocol (see [Section 4.3.1](#))
- Combination immunosuppressant medications not allowed in the inclusion and exclusion criteria (see [Section 4.1](#))
- Grade >2 AST or ALT elevation: (AST or ALT >3×ULN) in combination with total bilirubin >2×ULN or clinical jaundice as defined by Hy's Law
- Grade ≥3 AST or ALT elevation: (AST or ALT >5×ULN)
- Grade 4 Neutropenia: ANC <500/mm³
- Grade 4 Lymphopenia: ALC <200/mm³
- Grade 4 Thrombocytopenia: platelet count <25,000/mm³
- Pregnancy
- Malignancy (with the exception of non-serious local and resectable basal or squamous cell carcinoma of the skin)
- An episode of torsades de pointes

Patients must discontinue study treatment if they are receiving any treatments that are not specifically permitted in this protocol (see [Section 4.3.1](#)) and approved by the Medical Monitor.

Investigators may discontinue study treatment for:

- Any medical condition that the investigator or Sponsor determines may jeopardize the patient's safety if he or she continues to receive study treatment
- Investigator or Sponsor determines it is in the best interest of the patient
- Patient non-compliance

The primary reason for study treatment discontinuation should be documented on the appropriate eCRF. Patients who discontinue study treatment prematurely will not be replaced.

In some cases, study treatment may be resumed if approved by both the investigator and the Medical Monitor.

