4.5.2 Patient Discontinuation from Study

Patients have the right to voluntarily withdraw from the study at any time for any reason. In addition, the investigator has the right to withdraw a patient from the study at any time. Reasons for withdrawal from the study may include, but are not limited to, the following:

- Patient withdrawal of consent at any time
- Any medical condition that the investigator or Sponsor determines may jeopardize the patient's safety if he or she continues in the study
- Investigator or Sponsor determines it is in the best interest of the patient
- Patient non-compliance, as per Principal Investigator's discretion
- Study termination or site closure

Every effort should be made to obtain information on patients who withdraw from the study. The primary reason for withdrawal from the study should be documented on the appropriate eCRF. However, patients will not be followed for any reason after consent has been withdrawn. Patients who withdraw from the study will not be replaced.

If a patient discontinues the study prior to the Week 48 treatment completion visit, an early termination visit should be conducted. If possible, the investigator will clarify the following:

- If the patient withdrew consent for the remaining study procedures OR
- If the patient withdrew consent for the remaining study procedures as well as the use of all banked samples OR
- If the patient withdrew consent for the remaining study procedures as well as all use of study acquired clinical and laboratory data

These patients should return for the 8-week safety follow-up visit in this study (see [Appendix 1](#)). If the patient is unable to return for a follow-up visit, the trial site may contact the patient by telephone to determine their clinical status.

Patients who discontinue the study during the safety follow-up period but prior to completion of the 8-week safety follow-up will be asked to return to the clinic within 30 days (± 7 days) after the last dose of study drug or last scheduled visit for an early termination visit.

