6.5 EFFICACY ANALYSES

Patient efficacy data will be summarized separated by treatment cohort during the blinded study (GA30044), in addition to overall summaries. Efficacy summary will be based on the intent-to-treat population, defined as all eligible patients enrolled into this OLE study. Analyses of additional study populations (e.g., completers and per protocol [excluding major protocol violators]) will be performed as supportive evaluations. Additional subgroup analyses may be conducted on an exploratory basis. Details will be provided in the data analysis plan.

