Appendix 1 Schedule of Activities (cont.)

- ^c Patients will receive a telephone call from study staff to follow up for assessment of adverse events and concomitant medications.
- ^d At an unscheduled visit, adverse events and concomitant medications must be assessed. All other assessments are to be performed only if medically indicated based on the reason for the unscheduled visit. If the patient returns for an unscheduled visit or regular study visit and has any evidence of increased SLE-activity requiring treatment, perform all assessments required for a flare visit.
- ^e A flare visit is any unscheduled visit where the patient may require escalation of treatment for increased SLE activity. Assessments are to be performed only if medically indicated based on the reason for the flare visit.
- ^f Patients entering the OLE study may be consented after meeting entry criteria for Study GA30066, which may include use of qualifying test results from the Week 44 visit or later from Study GA30044 (see Section 4.4.1).
- ^g Starting at Day 1, all patients must record their OCS use as instructed by study staff (see Section 4.2.2.4).
- ^h Includes respiratory rate, pulse rate, temperature, and systolic and diastolic blood pressure while the patient is in a seated position for at least 5 minutes.
- ⁱ Includes an evaluation of the head, eyes, ears, nose, and throat, and the cardiovascular, dermatological, musculoskeletal, respiratory, gastrointestinal, genitourinary, and neurological systems. Any abnormality identified at baseline should be recorded on the General Medical History and Baseline Conditions eCRF. Particular attention should be given to evaluation of potential manifestations of active SLE (see [Appendix 9](#) BILAG-2004 Index; [Appendix 10](#) SLEDAI-2K; and [Appendix 12](#) CLASI) and of infections or other medical conditions, which could place the patient at increased risk.
- ^j Limited, efficacy assessment-directed or symptom-directed physical examinations should be performed that also allow for completion of SLEDAI-2K and BILAG-2004 assessments. Changes from baseline abnormalities should be recorded in patient notes. New or worsened clinically significant abnormalities should be recorded as adverse events on the Adverse Event eCRF.

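### The SLICC/ACR Damage Index and the GTCI are scheduled at neither early termination nor safety follow-up, so patients who stop early have no closing score on either index

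*Combined protocol and SAP*

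**What the plan says.** Table 1 (Section 2) lists, among the exploratory efficacy endpoints, "Change in SLICC/ACR Damage Index up to Week 48" and glucocorticoid toxicity by GTCI at Weeks 12, 24, 36 and 48. In Appendix 1 the corresponding rows are "SLICC damage index" (Day 1, Weeks 24 and 48) and "GTCl and fasting lipids" (Day 1, Weeks 12, 24, 36 and 48). Both rows are blank after Week 48: nothing at SFU, unscheduled, flare or ET visits. The rows for BILAG-2004, SLEDAI-2K with SFI, CLASI, PGA and Patient's Global Assessment are marked in all four of those columns.

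Patients leave by two routes. Section 4.5.1 covers stopping drug: "Patients must discontinue study treatment and return for a safety follow-up visit if they experience any of the following". Section 4.5.2 covers leaving the study: "If a patient discontinues the study prior to the Week 48 treatment completion visit, an early termination visit should be conducted", followed by the 8-week safety follow-up visit. No section tells a patient who is off drug to keep the regular Week 12 to Week 48 visits.

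Section 4.4.5.4 states the property of the Damage Index that matters here: "Damage is defined as non-reversible change not related to active inflammation". On analysis, Section 6.5 says "Efficacy summary will be based on the intent-to-treat population, defined as all eligible patients enrolled into this OLE study". It gives no missing-data rule for these endpoints and leaves details to a data analysis plan.

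**The concern.** The plan takes a closing score on five disease measures when a patient leaves early, but not on these two, and gives no reason. The efficacy summaries are meant to cover every eligible enrolled patient, yet for some of them no change score can exist. An analysis plan written later can choose how to handle a missing score but cannot recover one that was never taken.

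The gap matters more because some reasons for stopping overlap with what the indices record. Malignancy is a mandatory stop in Section 4.5.1 (with an exception for certain skin cancers) and also a Damage Index item in Appendix 8. Under Section 4.2.2.3.4, a patient whose SLE activity needs more than the permitted escape therapy is to come off drug and go to safety follow-up. If such patients have accrued more damage or steroid toxicity than those who complete, summaries built on the scheduled scores would look more favourable than the enrolled population warrants.

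**Working it through.** There is no planned figure to reproduce: Section 6.1 gives a maximum of about 240 patients, no sample size calculation and no dropout rate. The check is a reading of the schedule, then an illustration of size.

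**Schedule.**

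| Row in Appendix 1 | Treatment-period visits | SFU | ET |
|---|---|---|---|
| SLICC Damage Index | Weeks 0, 24, 48 | no | no |
| GTCI and fasting lipids | Weeks 0, 12, 24, 36, 48 | no | no |
| CLASI | Weeks 0, 4, 12, 24, 36, 48 | yes | yes |
| BILAG-2004 | Weeks 0, 4, 8, 12, 24, 36, 48 | yes | yes |

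A flare visit does not fill the gap. Neither index is marked there, and the footnote adds "Assessments are to be performed only if medically indicated based on the reason for the flare visit".

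**Illustration.** Inputs: N = 240 (Section 6.1); an assumed early-stop fraction d of 0.10 to 0.30, which the documents do not supply; stops spread evenly over 48 weeks; no regular visits after stopping.

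- No Week 48 score on either index: N × d
- No post-baseline Damage Index (stop before Week 24): N × d × 24/48
- No post-baseline GTCI (stop before Week 12): N × d × 12/48

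| d | No Week 48 score | No post-baseline Damage Index | No post-baseline GTCI |
|---|---|---|---|
| 0.10 | 240 × 0.10 = 24 | 24 × 0.5 = 12 | 24 × 0.25 = 6 |
| 0.20 | 240 × 0.20 = 48 | 48 × 0.5 = 24 | 48 × 0.25 = 12 |
| 0.30 | 240 × 0.30 = 72 | 72 × 0.5 = 36 | 72 × 0.25 = 18 |

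The other half of the early stoppers have a Week 24 Damage Index that is, on average, (48 − 24)/2 = 12 weeks old when they stop.

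**What a closing Damage Index could add.** Appendix 8 requires most items to have been present for at least 6 months, about 26 weeks. A manifestation that begins after Day 1 has lasted at most 20 weeks at a Week 20 ET visit, and at most 20 + 8 = 28 weeks at the follow-up visit. A closing score would therefore pick up little new persistent damage from a short stay. The scheduled Week 24 score has the same limit (24 < 26). What remains is of three kinds:

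- items scored as *ever* having occurred, such as myocardial infarction, significant tissue loss and upper gastrointestinal surgery;
- malignancy, for which the glossary asks for pathological documentation;
- damage that began before Day 1 and has since met the duration rule.

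**What a closing GTCI needs.** Weight, vital signs, concomitant medications and adverse events are already marked at ET, which covers the BMI, blood pressure and infection inputs. The myopathy, skin and neuropsychiatric items need no blood sample, and Appendix 3 sets a default when bone density is not measured. The main gaps are HbA1c and LDL.

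**The case against.** The case for leaving the schedule alone has real substance.

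Both endpoints are exploratory, in an uncontrolled extension. The underlying events are not lost to safety: adverse events are collected until 8 weeks after the last dose (Section 5.3.1), and all malignancies are adverse events of special interest (Section 5.2.3). That stands and limits the importance of the point. It does not supply a scored index.

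A reader might infer that patients given extra steroid drop out of the scores. Section 4.2.2.3.4 says otherwise. Patients given IV steroids, oral doses above the burst limit, or new or raised permitted immunosuppressants may stay on drug, so they keep their scheduled visits. Only treatment beyond that forces a stop. Many other mandatory stops, such as liver tests, cytopenias and pregnancy, have no evident link to either index.

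A reader might also infer that the mean change is biased, or that both endpoints describe mainly patients who stay on drug. Neither is shown. The figures above count missing scores and do not estimate a shift in any mean. Even at d = 0.30, (240 − 36)/240 = 85% of patients have a post-baseline Damage Index and (240 − 18)/240 = 92.5% a post-baseline GTCI. The second reading is fair only for the Week 48 values.

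Finally, it is tempting to carry the closing value forward as the last available score. For accumulating damage, a short-exposure score can still understate Week 48. The GTCI contains components that can improve (BMI, glucose, blood pressure, LDL) and is defined at fixed weeks, so a value taken after stopping does not stand in for one of them. The argument from irreversibility holds for the Damage Index only.

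**Conclusion.** The point holds as a gap in data collection. Neither index is taken at ET or SFU, so no early stopper has a closing score, those who stop before Week 24 have no post-baseline Damage Index, and those who stop before Week 12 have no post-baseline GTCI. With 10% to 30% of 240 stopping evenly over 48 weeks, that is 12 to 36 patients for the Damage Index and 6 to 18 for the GTCI. Both the rate and the even spread are assumptions.

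Because some stopping reasons overlap with the content of the indices, the two exploratory endpoints may understate damage and steroid toxicity. The direction is an inference from the stopping rules, and its size cannot be derived from the documents. Primary safety and SRI-4 are unaffected. The change is worth making because it is cheap and cannot be made up afterwards; the trial's main conclusions do not depend on it.

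**What to change.** In Appendix 1, mark the SLICC Damage Index in the ET column, and in the SFU column for patients who stopped drug before Week 48 and had no ET visit. Since damage does not reverse, the closing score is a valid lower bound for damage at Week 48 and should be described as such.

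Mark the GTCI in the ET column only. If the patient has not fasted, complete the items that need no fasting sample. Report the result as an end-of-participation value, separate from the Weeks 12, 24, 36 and 48 summaries, and do not substitute it for a fixed-week score. The data analysis plan should state this, and should give the number of patients with no post-baseline value on each index.

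The cost is two schedule rows and, for early stoppers only, two forms and possibly one HbA1c/lipid tube, at visits the protocol already provides for. Patients who withdraw consent, or who are reached only by telephone, will still have no closing score.
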